6.7.2. Historical Illness and Preexisting Conditions

Historical illness/condition is defined as the condition/event recorded on the Pre-Existing Conditions and Medical History eCRF page or on the Prespecified Medical History eCRF page with an end date prior to the date of informed consent. Preexisting condition is defined as the condition/event recorded on the Pre-Existing Conditions and Medical History eCRF page or on the Prespecified Medical History eCRF page with a start date prior to the date of informed consent, and no end date (that is, the event is ongoing) or an end date on or after the date of informed consent. Notice if a preexisting condition worsens in severity on or after the date of informed consent, it will be recorded as an AE on Adverse Events eCRF page from the date of worsening onwards. Historical illnesses and preexisting conditions will be classified using the latest version of the MedDRA. The number and percentage of patients with historical illnesses and preexisting conditions will be provided by treatment group, overall and by SOC and PT using the mITT population. Note that conditions with a partial or missing start date will be assumed to be “not preexisting” unless there is evidence, through comparison of partial dates, to suggest otherwise. Patients will only be counted once if same PT is listed in 2 or more different SOC categories.

6.8. Participant Disposition

A detailed description of participant disposition will be provided, including a summary of the number and percentage of participants entered into the study and randomized, the number and percentage of participants who complete the study or discontinue, both overall and by reason for discontinuation, and the frequency and percentage of patients who discontinue study treatment. A summary of important protocol deviations will be provided.

6.9. Concomitant Therapy

Previous and concomitant medications will be summarized by treatment group and will be presented by ATC drug classes using the latest version of the World Health Organization drug dictionary.

Under the composite estimand strategy described in Section 6.5.1, a patient will be considered a nonresponder after the first occurrence of a violation of any of the following concomitant medication rules, regardless of the patient's efficacy status or disposition status:

- no initiation or increase in dose from baseline of
 - nonsteroidal anti-inflammatory drug intended for treatment of signs and symptoms of SLE
 - prednisone (or equivalent)
 - antimalarial. and
 - immunosuppressant
- prednisone ≤ 10 mg/day (or equivalent) by Week 12

Violations of concomitant medication rules will be first identified via programming and then reviewed by a blinded medical to confirm the violations align with the criteria specified in the protocol. The confirmed list provided by the blinded medical will be used for analyses.

6.9.1. Corticosteroids

To allow for assessments of changes in doses of various corticosteroids, it was necessary to standardize all corticosteroid doses to an equivalent prednisone dose. Table KFAJ.6.2 provides a summary of frequent corticosteroids and their prednisone-equivalent dose. The dose of the drug listed in Column 1 is multiplied by the conversion factor in Column 2 to provide the prednisone equivalent dose (in milligrams). This dose of corticosteroid will be referred to as “prednisone (or equivalent)” throughout this document.

See Appendix 3 for a complete table showing conversion factors for each corticosteroid medication identified during the study, instructions for selecting corticosteroids, and the manual review process. References for this table can also be found in Appendix 3.

Baseline prednisone (or equivalent) dose will be the total daily dose of all corticosteroids being taken by a patient at Visit 2. This baseline dose will be used for baseline summaries and for comparisons to later visits. A daily dose of prednisone (or equivalent) will be calculated for each day between baseline and treatment discontinuation. The daily dose of prednisone (or equivalent) at each visit date will be used as the corticosteroid dose for that visit.

6.10. Treatment Compliance

Patient compliance with study medication will be assessed from the randomization visit (Week 0) to Visit 15 (Week 24) during the treatment period. Compliance will be summarized from randomization until end of treatment using the mITT population. A patient is considered noncompliant if 2 or more of the prescribed doses during the study are missed, not including doses withheld by the investigator. A patient who takes more than 12 of the prescribed doses during the treatment period is also considered noncompliant.

Compliance to study drug in the period of interest will be calculated as follows:

$$\frac{\text{actual total \# of doses}}{\text{Expected total \# of doses}} * 100.$$

If a patient has a dose temporarily interrupted by the investigator during the period, the total number of days that drug was withheld will be deducted from the total number of days in the calculation of the expected total number of doses used.

The summary statistics of the percent of compliance and noncompliance rate will be summarized by treatment group. The percent of compliance for Week 0 (Visit 2) through Week 24 (Visit 15) will be presented, along with the associated noncompliance rates.

6.11. Handling of Dropouts or Missing Data

Missing data imputation is handled separately from the estimand strategy. After intercurrent events are accounted for according to an estimand strategy described in Section 6.5, any remaining missing data will be handled using missing data imputation methods described in this section. Reasons for such missing data include, but are not limited to,

- intermittent missing visits, assessments, or some components of assessments
- temporary treatment interruptions, and
- early treatment discontinuation.

When NRI is used, missing binary data will be imputed as non-response.

When last observation carried forward is used, missing continuous data will be imputed with the last nonmissing postbaseline observation prior to the first occurrence of intercurrent events. For patients without at least one postbaseline observation, missing continuous data will not be imputed.

When baseline observation carried forward is used, missing continuous data will be imputed with baseline observation (last nonmissing data before the first injection). For patients without baseline observation, missing continuous data at postbaseline visits will not be imputed.

The missing data imputation methods for planned analyses are specified in Sections 6.14, 6.15, and 6.16.

6.12. Multicenter Studies

This study will be conducted by multiple investigators at multiple sites internationally. The countries will be categorized into geographic regions, as described in Section 5.2. Geographic region will be included in a statistical model as a fixed effect, unless otherwise specified.

6.13. Multiple Comparisons/Multiplicity

No adjustments for multiplicity will be made for any analyses in this study.

6.14. Primary Endpoint/Estimand Analyses

The primary efficacy endpoint per composite estimand strategy (the primary estimand as described in Section 6.5.1) is

- SLEDAI-4 at Week 24 after accounting for violation of concomitant medication rules: (i) initiating or increasing in dose of corticosteroids, antimalarial, or immunosuppressant, or (ii) using prednisone >10 mg per day (or equivalent) after Week 12

Under the composite estimand strategy, participants will be considered nonresponders at all subsequent visits after the first violation of concomitant medication rules regardless of their discontinuation status.

The primary analysis for treatment comparison of each LY3471851 dose with placebo will be analyzed using a logistic regression model with treatment group, baseline disease activity (SLEDAI-2K <10; SLEDAI-2K ≥10), corticosteroid dose at baseline (<10 mg/day or ≥10 mg/day), and geographic region (North America, Latin America, Europe, Asia, Japan, Rest of World) in the model. The analysis will be based on the mITT population and missing data will be handled using NRI. P-values from the Fisher's exact test will also be reported as a sensitivity analysis, when logistic regression sample size requirements are not met (<5 subjects in any category for any factor).

As supplementary analyses,

- to determine the impact of important protocol deviations, the primary analysis detailed above will also be conducted on the per-protocol population

CCI

6.15. Secondary Endpoints/Estimand Analyses

The secondary endpoints per composite estimand strategy (the primary estimand as described in Section 6.5.2) without violation of concomitant medication rules: (i) initiating or increasing in dose of corticosteroids, antimalarial, or immunosuppressant, or (ii) using prednisone >10 mg per day (or equivalent) after Week 12 are

- BICLA at Week 24
- SRI-4 at Week 24, and
- LLDAS at Week 24.

Under the composite estimand strategy, participants will be considered nonresponders at all subsequent visits after the first violation of concomitant medication rules regardless of their discontinuation status.

The analytical details specified in Section 6.14 will be followed. The supplementary analyses in Section 6.14 may also be considered for the secondary efficacy endpoints if deemed appropriate.

Description and derivation of secondary endpoints are described in a separate document, and the handling of missing data due to, for example, a missed visit is detailed in [Appendix 1](#).

The image shows the letters 'CCI' in a large, bold, red serif font. The letters are set against a solid black rectangular background. The 'C' is on the left, the first 'I' is in the middle, and the second 'I' is on the right. The font is classic and elegant, with a slight shadow or depth to the letters.

The image shows a large, stylized logo consisting of the letters 'C', 'C', and 'I' in a red, serif font. The letters are set against a solid black rectangular background that occupies most of the page. The 'C's are thick and rounded, and the 'I' is a simple vertical bar with a small serif at the top.

6.19. Safety Analyses

All safety data will be descriptively summarized by treatment groups and analyzed based on the safety population. The safety population is defined as those patients who received at least 1 dose of study drug and did not discontinue the study for the reason “lost to follow-up” at the first postbaseline visit. The safety analyses include AEs, safety in special groups and circumstances, including adverse events of special interest, laboratory analytes, QIDS-SR16, C-SSRS, ECGs, and vital signs. The duration of exposure will also be summarized. The categorical safety measures will be summarized using IRs and analyzed by Fisher’s exact test. The mean change in the continuous safety measures including vital signs, QIDS-SR16, physical characteristics, and laboratory values will be summarized by visits and analyzed by ANCOVA, with treatment and baseline values in the model. More details are provided in subsequent sections.

Not all displays described in this section will necessarily be included in the CSRs. Any display described and not provided in the CSR would be available upon request. Not all displays will necessarily be created as a “static” display. Some may be incorporated into interactive display tools instead of or in addition to a static display. Any display created interactively will be included in the CSR if deemed relevant to the discussion.

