6.1. Study Interventions Administered

Study interventions

This study involves 3 dose levels of LY3471851 and placebo, as shown.

Treatment Name	LY3471851	Placebo
Dosage Formulation	CCI	0.9% sodium chloride
Dosage Levels		not applicable
Routes of Administration	subcutaneous injection	subcutaneous injection
Dosing Instructions	Dosing every 2 weeks	Dosing every 2 weeks

LY3471851 drug product will be provided as a sterile solution in a vial for SC injection. The drug product vials will be supplied in cartons, with the appropriate quantity specific to the planned dispensing schedule of the investigation product (IPs). Dosing solutions will be prepared at each clinical study site by an unblinded pharmacist (or other unblinded qualified individual) and loaded into syringes for SC dosing (see Section 6.3 on blinding). When the dosing solutions are prepared according to the provided instructions, it will not be possible to distinguish LY3471851 from placebo.

Monitoring after dose administration

All participants should be monitored for 30 minutes or longer after dosing, according to investigator practice or local standard of care.

Packaging and labeling

LY3471851 will be supplied by the sponsor or its designee in accordance with current Good Manufacturing Practice (cGMP). Clinical trial materials will be labeled according to the country's regulatory requirements. All IPs will be stored, inventoried, reconciled, and destroyed according to applicable regulations.

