9.3. Populations for Analyses

The mITT population, which includes all randomized participants receiving at least 1 dose of study intervention, will be used in analyses of efficacy and patient-reported outcomes (PRO), unless otherwise noted in the SAP).

The following populations are defined for this study:

Population	Description
Entered	All participants who sign the informed consent form
Modified Intent-to-Treat (mITT)	All participants randomly assigned to study intervention and who take at least 1 dose of study intervention. Participants will be analyzed according to the intervention to which they were assigned.
Safety	All participants randomly assigned to study intervention and who take at least 1 dose of study intervention. Participants will be analyzed according to the intervention they actually received within each study period.
Pharmacokinetic (PK) Analysis	All participants randomly assigned to study intervention and who take at least 1 dose of study intervention and have PK data available.

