6.19.1. Extent of Exposure

Duration of exposure to study drug will be summarized for the safety population by treatment group. Exposure will be calculated as the date of last dose of study drug (or date of discontinuation) minus the date of first dose of study drug plus 1 day. Total PYs of exposure will be reported for each treatment group for overall duration of exposure. Descriptive statistics (n, mean, SD, minimum, first quartile, median, third quartile, and maximum) will be provided for patient-days of exposure and the frequency of patients falling into different exposure ranges will be summarized. Exposure ranges are as follows:

- ≥ 4 weeks, ≥ 12 weeks, and ≥ 24 weeks
- >0 to <4 weeks, ≥ 4 weeks to <12 weeks, ≥ 12 weeks to <24 weeks, and ≥ 24 weeks

Overall exposure will be summarized in total PYs, which are calculated according to the following:

Exposure in PYs = sum of duration of exposure in days (for all patients in treatment group) / 365.25

No p-values will be reported in these tables as they are intended to describe the characteristics of the study sets.

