6.19.2. Adverse Events

6.19.2.1. Adverse Events

AEs are recorded in the eCRF. Each AE will be coded to SOC and PT, using the MedDRA version that is current at the time of database lock. Severity of AEs is recorded as mild, moderate, or severe.

TEAEs are defined as events that either first occurred or worsened in severity after the first dose of study drug and the earliest of the visit study drug disposition date or the last visit date during the treatment period, whichever occurred first, and up to 30 days after study treatment discontinuation. The MedDRA LLT will be used in defining which events are treatment-emergent. The maximum severity for each LLT during the baseline period until the first dose of the study medication will be used as baseline. If an event is preexisting during the baseline period, but it has missing severity, and the event persists during the treatment period or up to 30 days after treatment discontinuation, then the baseline severity will be considered mild for

determining any postbaseline treatment-emergence (that is, the event is treatment-emergent unless the severity is coded mild at postbaseline). If an event occurring postbaseline has a missing severity rating, then the event is considered treatment-emergent. Should there be insufficient data for an AE start date to make this comparison (for example, the AE start year is the same as the treatment start year, but the AE start month and day are missing), the AE will be considered treatment-emergent. For events occurring on the day of the first dose of study treatment, the day and time of the onset of the event will both be used to distinguish between pretreatment and posttreatment in order to derive treatment-emergence.

In general, summaries will include the number of patients in the safety population (N), frequency of patients experiencing the event (n), and relative frequency (that is, percentage; $n/N*100$).

In an AE overview table, the number and percentage of patients in the safety analysis set who experienced death, an SAE, any TEAE, permanent discontinuation from study drug due to an AE, temporary interruption of study drug due to an AE or laboratory abnormality, or a severe TEAE will be summarized by treatment group.

The number and percentage of patients with TEAEs will be summarized by treatment group in 2 formats listed below. For events that are gender specific, the denominator and computation of the percentage will only include patients from the given gender.

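### The SAP safety population drops dosed participants recorded as lost to follow-up at the first postbaseline visit, whereas the protocol keeps everyone dosed

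*SAP*

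**What the plan says.** Protocol 9.3 defines the safety population by one condition beyond randomization: "All participants randomly assigned to study intervention and who take at least 1 dose of study intervention". It assigns arms as treated: "Participants will be analyzed according to the intervention they actually received within each study period". Protocol 9.4.5 bases the safety analyses on that population.

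SAP 6.6 (Safety row) and the opening paragraph of SAP 6.19 both require in addition that the participant "did not discontinue the study for the reason “lost to follow-up” at the first postbaseline visit". SAP 6.19 uses this population for all safety data. SAP 6.19.1 states: "Duration of exposure to study drug will be summarized for the safety population by treatment group". SAP 6.19.2.1 takes its size as N for the adverse event percentages, and builds the overview table (deaths, SAEs, TEAEs, severe TEAEs, discontinuations and interruptions) on the safety analysis set.

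The mITT population in SAP 6.6 carries no such exclusion.

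**The concern.** Membership of a safety population should be settled by exposure. Here it also depends on something that happens after dosing, and it ignores whether an event was recorded.

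An excluded person need not be empty of safety data. Protocol 6.1 says: "All participants should be monitored for 30 minutes or longer after dosing". Adverse events are collected from consent onward (Protocol 8.3.1). SAP 6.19.2.1 plans for events on that day: "For events occurring on the day of the first dose of study treatment, the day and time of the onset" decide whether such an event is treatment-emergent. An event seen on site after the first injection therefore meets the SAP's own TEAE definition, and the population rule then removes it.

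At stake is agreement between the two documents on the denominator of the main safety tables, and the completeness of the tabulated first-dose experience. The SAP's populations also fit together poorly. Under nonresponder imputation (SAP 6.14) the same person counts as a nonresponder in the primary analysis and appears in the baseline tables (SAP 6.7.1), yet is missing from the exposure and adverse event tables.

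**Working it through.** **Definitions side by side**

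| Condition | Protocol 9.3 | SAP 6.6 and 6.19 |
|---|---|---|
| Randomized | yes | yes |
| At least one dose | yes | yes |
| Not lost to follow-up at the first postbaseline visit | not required | required |

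The first postbaseline visit is Visit 3 at Week 1 (Protocol 1.3), with no dosing at that visit. An excluded participant has therefore had the Visit 2 dose only.

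**Inputs.** The arm size of 70 is from Protocol 9.2. The number excluded per arm, k, is in neither document; I assume 0 to 3. The event counts below are also assumed, for illustration.

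**The plan's own figure.** The only design figure is power of at least 80% with 70 per group (Protocol 9.2), for response rates of 0.40 and 0.64 (SAP 6.1). With pooled variance under the null and no continuity correction:

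power = Φ[(0.24 × √70 − 1.96 × √(2 × 0.52 × 0.48)) / √(0.40 × 0.60 + 0.64 × 0.36)] = Φ[(2.008 − 1.385) / 0.686] = Φ(0.909) = 81.8%.

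This reproduces the stated figure. The issue does not touch it, because efficacy uses mITT.

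**Share of an arm removed.** k/70: 0% for k = 0, 1/70 = 1.4% for k = 1, 3/70 = 4.3% for k = 3.

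**Event rates**

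| Case | Protocol set | SAP set |
|---|---|---|
| 5 events; 3 excluded, none with the event | 5/70 = 7.1% | 5/67 = 7.5% |
| 5 events; 1 excluded, who had one of them | 5/70 = 7.1% | 4/69 = 5.8% |
| 1 event; 1 excluded, who had it | 1/70 = 1.4% (95% CI 0.04 to 7.7%) | 0/69 = 0% (upper limit 5.2%) |

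Intervals are two-sided Clopper-Pearson. The rate can move either way.

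**Chance that an event is lost.** Suppose exclusion is unrelated to having the event, and the event is one an excluded person could have on record, in practice a first-dose-day event.

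- One event in the arm: k/70, so 1.4% for k = 1 and 4.3% for k = 3.
- Two participants with the event: 1 − (69 × 68)/(70 × 69) = 2.9% for k = 1; 1 − (67 × 66)/(70 × 69) = 8.4% for k = 3.

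For events that accrue over the whole 24 weeks the chance is smaller, because an excluded person was barely observed.

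**Exposure.** SAP 6.19.1 counts last dose (or discontinuation) minus first dose plus one day. A completer last dosed on Day 155 has 155 days, so 70 completers have 70 × 155 = 10,850 patient-days. An excluded person contributes 1 day (last dose) or about 8 (discontinuation at Day 8). With k = 3 that is 3/10,850 = 0.03% or 24/10,850 = 0.2%. The effect on total exposure is negligible; what changes is the count of people exposed.

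**The case against.** The strongest reply has four parts.

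1. *The protocol allows it.* Protocol 9.4.1 lets the SAP change analysis methods without an amendment unless a principal feature is affected, provided the SAP and clinical study report describe and justify the change. The clause appears in the same terms in two places, so it looks deliberate. I see no justification in the visible text, but parts of the SAP are removed or blacked out, so I do not say that none exists. Permission to change a method does not make this exclusion sound.

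2. *The group is tiny and hardly observed.* Protocol 7.3 reserves the term for people who keep missing visits and cannot be reached, and Protocol 7.2 expects withdrawal to be uncommon. Keeping such people in N counts them as event-free after little follow-up. This stands as a reason to expect a small effect, and zero exclusions is possible. It does not justify dropping an event already on record. Protocol 7.3 also raises a practical question: the visible text does not say how a status based on repeated absence is tied to a single Week 1 visit.

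3. *The data remain visible elsewhere.* Largely true. The listings of all AEs and all SAEs (SAP 6.19.2.2), the malignancy listing (6.19.3.3), the registry summary (6.20.4) and disposition by reason (6.8) are worded more widely. The eDISH plot (6.19.5.1) is too, though it needs a postbaseline value that these people would usually lack. What is lost is the tabulated count, not the record.

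4. *The loss probabilities are generous.* Accepted: they apply to first-dose-day events only, as stated above.

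**Conclusion.** The concern holds. The protocol and SAP give different safety populations, and the narrower one governs the main exposure and adverse event summaries through a condition that arises after dosing. The textual conflict is certain; the numerical effect is probably small. On the assumption of 0 to 3 exclusions per arm of 70, at most 4.3% of an arm is removed. The change in denominator alone is minor, and the larger risk is that a rare first-dose event disappears from a summary table. The documents do not show that this kind of loss is related to tolerability, so no direction of bias is claimed. Participants who stay in the set lose no data, and efficacy and power do not change. The point should be corrected because the conflict is clear and the correction is cheap, not because a large distortion is expected.

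**What to change.** In both SAP 6.6 (Safety row) and SAP 6.19, delete the added condition that the participant "did not discontinue the study for the reason “lost to follow-up” at the first postbaseline visit", so that both sections match Protocol 9.3. Leave the exposure formula in SAP 6.19.1 and the TEAE window in SAP 6.19.2.1 as they are. Where an analysis needs a postbaseline value, as for laboratory tests and vital signs, state that requirement in that analysis.

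If the sponsor wants to keep the restricted set, use it only as a labelled sensitivity set and list the excluded participants by arm.

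The cost is the same deletion in two sections, with no new data. The one downside is that percentages fall slightly if the restored participants had no events, for example from 5/67 = 7.5% to 5/70 = 7.1%.
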